1.2 Diagnostic criteria

1.2.1 Diagnostic criteria for TCM

According to the Technical Guidelines for Clinical Research on New Chinese Medicines for Stroke issued by the State Food and Drug Administration in 2015, the diagnostic points of stroke disease and its disease categories are as follows:

Disease diagnosis:

(1) The main symptoms are sudden fainting, unconsciousness, distorted mouth and eyes, poor or unspoken speech, numbress of the paraplegic body, or only hemiplegia, distorted mouth and eyes, and unfavourable speech without fainting;

(2) Acute onset and rapid development, similar to the characteristics of 'wind' in nature;

(3) Symptoms and signs last for more than 24 hours;

(4) Most often occurs in people over 40 years of age.

Diagnosis of disease categories:

(1) Middle meridian: meets the diagnostic criteria of Chinese medicine for stroke, but there is no mental disorder;

(2) Middle viscera: those who meet the diagnostic criteria for stroke in Chinese medicine, but have delirious disorder.

1.2.2 Western medicine diagnostic criteria

According to the Chinese Guidelines for Diagnosis and Treatment of Acute Ischaemic Stroke 2018 issued by the Cerebrovascular Group of the Neurology Division of the Chinese Medical Association in 2018, the diagnostic points of acute ischaemic stroke (acute cerebral infarction) are as follows:

(1) Acute onset;

(2) Focal neurological deficits, and in a few cases, comprehensive neurological deficits;

(3) Symptoms or signs lasting for an unlimited period of time, or more than 24 hours;

(4) Exclusion of non-vascular causes;

(5) Brain CT/MRI to exclude cerebral haemorrhage.

1.3 Inclusion criteria

Inclusion criteria

(1) Meet the diagnostic criteria for ischemic stroke in the Chinese Guidelines for Diagnosis and Treatment of Acute Ischemic Stroke 2018.

(2) Comply with the diagnostic criteria for ischemic stroke in TCM.

(3) Within 2 weeks of acute onset of ischaemic stroke.

(4)  $4 \leq \text{NIHSS score} < 15$ .

(5) Age 40-80 years old.

Exclusion criteria

 Diagnosis of haemorrhage or other pathological brain diseases based on head CT or MRI;

(2) Allergy, allergy to the test drug or its related flavour or ingredients;

(3) Age <40 years or >80 years;

(4) Severe hepatic or renal impairment.

1.4 Intervention measures and treatment course

Treatment group: basic treatment + Chuanhong Zhongfeng Capsules

Control group: basic treatment (refer to China Acute Ischaemic Stroke Diagnosis and Treatment Guidelines 2018)

Treatment course: 14±2 days

1.5 Specific experimental steps

(1) Extraction of sample whole protein: extract sample whole protein using protein lysate, protease/modification inhibitor, ultrasonic crushing, high-speed centrifugation;

(2) Protein extraction quality control: use SDS-PAGE, BCA, Bradford and other methods to do preliminary analysis of the extracted sample proteins, in order to assess the parallelism between the samples, the presence of high abundance of proteins, the presence of protein degradation phenomenon, the protein concentration to meet the subsequent experiments and so on;

(3) Proteolysis: After the extracted proteins are deformed and reduced, trypsin is used to enzymatically digest the proteins to obtain peptide samples;

(4) Enrichment of modified peptide fragments: enrichment of modified peptide fragments in peptide samples with antibodies specific for the purpose of modification;

(5) Separation of peptide fractions: Using high performance liquid chromatography (HPLC) or enriching peptides obtained by enzymatic digestion or modified antibodies, peptide fractions are separated according to their abundance, in order to reduce the complexity of the sample and improve the sensitivity of mass spectrometry detection;

(6) Liquid-mass spectrometry analysis: The enriched peptide samples were analysed by Orbitrap Exploris 480 liquid-mass spectrometer to obtain raw data containing primary and secondary spectra;

(7) Spectrogram search data analysis: peptide samples containing modified peptides were identified and quantitatively analysed using Maxquant, Mascot and Proteome Discoverer software; (8) Bioinformatics analysis.

2 Feasibility analysis:

(1) Novel topic selection: This project adopts 4D Label-free proteomics technology and PRM technology to elucidate for the first time the mechanism of action and potential targets of Chuanhong Zhongfeng Capsule in the treatment of acute cerebral infarction, to provide a prospective basis for the precise medical treatment of this disease, and to provide a research direction for the prevention and treatment of cerebral infarction by traditional Chinese medicine compound. Therefore, this topic is feasible in terms of topic selection and theory.

(2) Sufficient preliminary work: [name], a national medical master, found that Chuanhong Stroke Capsule was effective in the treatment of stroke, reduced the disability rate, and improved the long-term prognosis of the patients in the National 8th Five-Year Plan 'Clinical and Experimental Research on Treatment of Stroke Disease with Traditional Chinese Medicine'. The project leader is conducting research on the proteomics technology of intracranial atherosclerotic stenosis in patients with acute cerebral infarction, and has a good understanding of proteomics technology. The project has a solid working foundation, which can ensure the smooth progress of the subsequent experiments.

(3) Reasonable research team: the project leader has been committed to clinical and basic research on acute cerebral infarction and has accumulated rich experience. The research team consists of 3 senior titles, 8 intermediate titles, 1 doctoral student and 1 master's student. The team members have the experience of hosting the National Natural Project and provincial and ministerial level projects, and are familiar with the domestic and international development of acute cerebral infarction and proteomics research; they have published many high-level articles, and are capable of completing the research of this project.

(4) Complete experimental conditions: This project will be carried out by PTM BIO.PTM BIO is committed to providing top proteomics services and high-quality antibody

reagents for global researchers and industrial customers. With the scientific background of 'proteomics - precision medicine', the company has formed an innovative business model integrating R&D, production and service, and has now built a proteomics, protein modification genomics technology platform, bioinformatics analysis platform, protein modification antibody development platform, high-efficiency rabbit monoclonal antibody development platform and big data platform. The company has established a proteomics and protein modification genomics technology platform, a bioinformatics analysis platform, a protein modification antibody development platform, a high-efficiency rabbit monoclonal antibody development platform and a big data platform. The company has instruments such as Orbitrap Exploris 480 liquid-mass spectrometer and software such as Maxquant, Mascot and Proteome Discoverer. The above research conditions and equipment can meet the needs of the experiment.

3.Innovative points

This study is the first to investigate the mechanism of action and potential targets of Chuanhong Zhongfeng Capsule in the treatment of acute cerebral infarction by using 4D Label-free proteomics technology and PRM technology.

(III) Annual programme progress and expected goals.

('Starting and ending years' are counted from the date of application, and the completion period is generally no more than 3 years).

First year/annual plan: collect patients for clinical enrolment and improve the study protocol.

Expected goal: Improve the study protocol and complete the collection of patient blood samples.

Year 2/annual plan: complete QC and total protein extraction, start mass spectrometry and raw letter analysis.

Expected goal: Proteomics data analysis.

Third year/annual plan: conduct PRM validation, article writing and report project summary report.

Expected goal: complete 1 SCI and 1 core journal paper.

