1.1 Research methods

In this project, 4D Label-free proteomics technology is applied, and the signal ratio (Ratio) of serum proteins in the treatment and control groups is used to measure the difference in their expression in different states, and the significance test T-test p value is calculated from the results of multiple repetitions of the experiment. when the Ratio is greater than the specified threshold and the p value is less than 0.05, the corresponding proteins can be considered to have significant differences in expression. the difference in expression of the corresponding protein can be considered significant. Then, the identified serum proteins were subjected to functional module analysis, clustering and then functional enrichment. The results of the analysis were more intuitive and detailed, and the functional correlation of the differentially expressed proteins in the comparative groups was found, and the expected related pathways were uncovered. Finally, PRM technology is applied to validate the candidate proteins and confirm their reproducibility and reliability as clinical biomarkers.

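### SAP sections 1.1 and 1.5 contradict each other on what is measured: serum protein expression, or peptides enriched by antibody for a modification that is never named

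*SAP*

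**What the plan says.** Section 1.1 fixes the analysed quantity: "4D Label-free proteomics technology is applied, and the signal ratio (Ratio) of serum proteins in the treatment and control groups". That Ratio serves as the measure of differential expression. A protein is a hit when its Ratio passes a threshold (no value given) and the t-test gives p below 0.05. Hits go on to clustering and functional analysis, and candidate proteins go to PRM. Section 1.1 mentions no protein modification.

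Section 1.5 sets out the laboratory steps:

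- Step (1): "extract sample whole protein using protein lysate, protease/modification inhibitor".
- Step (3): "trypsin is used to enzymatically digest the proteins to obtain peptide samples".
- Step (4): "enrichment of modified peptide fragments in peptide samples with antibodies specific for the purpose of modification". It carries no qualifier such as 'if applicable', and the modification is not named here or elsewhere.
- Step (5), on separating the peptides: "enriching peptides obtained by enzymatic digestion or modified antibodies".
- Step (6): "The enriched peptide samples were analysed by Orbitrap Exploris 480 liquid-mass spectrometer".
- Step (7): "peptide samples containing modified peptides were identified and quantitatively analysed".

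Section 2(1) describes the project again: "This project adopts 4D Label-free proteomics technology and PRM technology". The statement of innovation in section 3 names the same two techniques and no modification. In the annual programme, the second year covers quality control, extraction of total protein and mass spectrometry, with no enrichment stage.

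**The concern.** The two sections describe different measurements. An unenriched tryptic digest, quantified at protein level, estimates how much of each protein is present. A sample enriched by a modification-specific antibody estimates how much of the modified form is present, and that depends on two things: the amount of protein and the share of it that is modified.

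If the second measurement were fed into the rule of section 1.1, a hit could not be read as a difference in expression. A protein whose amount is unchanged could be declared differentially expressed because its occupancy changed, and a real change in amount could be hidden by an opposite change in occupancy. The functional analysis and the list of PRM candidates both rest on this Ratio. PRM as described tests only the candidates, so it could not recover a protein missed at the discovery stage.

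**Working it through.** The SAP has no figure to reproduce here. The check compares the two sections and then asks what the Ratio would estimate under each reading.

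**Step 1: the sections side by side.**

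| Item | Section 1.1 | Section 1.5 as written |
|---|---|---|
| Unit measured | Serum protein | Peptides enriched for a modification |
| Input to the spectrometer | Not specified | Enriched samples (step 6) |
| Quantified | Protein signal, treatment against control | Samples containing modified peptides (step 7) |
| Modification | None mentioned | Required by step (4), not named |
| Unenriched run or normalisation to total protein | Not mentioned | Not described |

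**Step 2: the Ratio from a plain digest.** Let P be the amount of a protein, with T for treatment and C for control. If protein-level quantification draws on many peptides and the modified share of the signal is small, then

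Ratio = P_T / P_C.

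This is the quantity that section 1.1 interprets.

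**Step 3: the Ratio from an enriched sample.** Let f be the occupancy and k a response constant for the peptide, including recovery in the enrichment, assumed equal in both groups. The signal is k × P × f, so

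Ratio = (k × P_T × f_T) / (k × P_C × f_C) = (P_T / P_C) × (f_T / f_C).

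On the log scale, log Ratio = log(P_T / P_C) + log(f_T / f_C). A test of the enriched signal therefore tests whether the sum of the two terms is zero. It is a test of expression only if f_T = f_C.

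**Step 4: what the identity implies.** The SAP gives no occupancies. The values below are assumptions that show only how the identity behaves.

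| True protein ratio | Occupancy, treatment against control | Enriched Ratio |
|---|---|---|
| 1.0 | 10% against 10% | 1.0 × 1.0 = 1.0 |
| 1.0 | 15% against 10% | 1.0 × 1.5 = 1.5 |
| 1.0 | 20% against 10% | 1.0 × 2.0 = 2.0 |
| 2.0 | halved (occupancy ratio 0.5) | 2.0 × 0.5 = 1.0 |

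With equal occupancy (first row) the enriched Ratio is correct. In the second and third rows an unchanged protein appears raised, and in the last a doubled protein appears unchanged. Because section 1.1 gives no value for the threshold, it cannot be said which of these ratios would count as a hit.

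**Step 5: does anything in the SAP reconcile the sections?** The 'or' in step (5) can be read to admit peptides straight from digestion, but steps (6) and (7) then speak only of enriched samples and samples containing modified peptides. Section 2(1), section 3 and the annual programme all point to ordinary protein-level work, but none withdraws or qualifies step (4). The contradiction remains.

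**The case against.** The strongest reply is that this is template wording with no bearing on the analysis. Much supports it. Section 1.1, which defines the comparison and its interpretation, speaks only of protein expression. Section 2(1), section 3 and the annual programme name label-free proteomics and PRM, with no modification and no enrichment stage. Section 2(4) says the work goes to an outside company with both proteomics and protein-modification platforms, which fits a shared description of workflow. Step (4) also cannot be carried out as it stands, since no antibody can be chosen for an unnamed modification.

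The wording of the other steps is looser than it looks at first. Step (5) uses 'enriching' for peptides from digestion as well, so 'enriched' in step (6) need not mean enriched by antibody. Step (7) does not say that only modified peptides are quantified. The conflict rests mainly on step (4).

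Most of this stands, and it makes a plain digest the likelier intent. It does not remove the conflict. Step (4) is unconditional, the company named has the platforms to perform it once someone picks a modification, and no text says that the Ratio comes from the unenriched digest.

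A reader might go further and infer that the trial will in fact quantify modified peptides, so that its protein results will be wrong. The SAP does not support that: it shows two incompatible descriptions, not a decision to enrich.

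**Conclusion.** The contradiction between sections 1.1 and 1.5 is certain from the text. Its effect is conditional. If the steps are followed as written, the Ratio mixes protein amount with occupancy and section 1.1's interpretation holds only if occupancy is equal in both groups. If the plain digest is quantified, which is the likelier intent, the Ratio is sound and only the laboratory steps are misdescribed.

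No size can be put on the possible error. A reader might want a rate of false or missed hits, but that would need occupancies, a standard deviation and a sample size, none of which the SAP gives, as well as a value for the threshold. The identity in the working is enough to show that the two readings lead to different conclusions. It assumes equal peptide response and recovery in both groups and, for the plain digest, a small modified share of the signal.

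This is an inconsistency to correct before laboratory work starts. It is not evidence of a flawed design.

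**What to change.** Before samples are processed, make section 1.5 agree with section 1.1:

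1. State in section 1.5 that the Ratio and t-test use protein-level quantification of the unenriched tryptic digest from step (3).
2. Delete step (4).
3. Remove the enriched and modified-peptide wording from steps (5) to (7).

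Only if a modification analysis is truly intended: name the modification, make it a separate secondary analysis, and normalise each site to its protein's abundance in the unenriched run.

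The first route costs only wording, provided processing has not begun. The SAP does not show the current status, but its annual programme puts blood collection in the first year and mass spectrometry in the second, which leaves a natural point for the correction. The second route costs the enrichment work, additional sample volume and a further run. The SAP gives no figures from which to price these.
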